Unanticipated Serious Adverse Device Effect (USADE) Ref: ISO 14155-2011 Ref: MEDDEV 2.7/3 12/2010	Serious adverse device effect which by its nature, incidence, severity, or outcome has not been identified in the current version of the risk analysis report. NOTE 1: Anticipated serious adverse device effect (ASADE) is an effect which by its nature, incidence, severity or outcome has been identified in the risk analysis report.
Device Deficiency Ref: ISO 14155-2011 Ref: MEDDEV 2.7/3 12/2010	A device deficiency is any inadequacy of a medical device with respect to its identity, quality, durability, reliability, safety or performance. NOTE 1: Device deficiencies include malfunctions, misuse or use errors, and inadequate labeling.

Underlying diseases are not reported as AEs unless there is an increase in severity or frequency during the course of the investigation. Death should not be recorded as an AE, but should only be reflected as an outcome of a specific SAE (see Table 20-1 for AE definitions).

Any AE experienced by the subject after informed consent, whether during or subsequent to the procedure, must be recorded in the eCRF.

Refer to Section 19 for the known risks associated with the device(s).

NOTES:

1. For the purposes of this study, hospitalization is defined as any in-patient admission.
2. Hospitalizations occurring for the purpose of performing a planned procedure as per routine care such as implant procedures, or follow-up visits, are not to be reported as a SAE. However, complications or adverse events that occur during the planned procedure should be reported as (S)AEs if they meet the protocol specified definitions.
3. Elective/planned hospitalization(s) need not be reported as an SAE. However, complications or adverse events that occur during an elective/planned hospitalization, should be reported as (S)AEs if they meet the protocol specified definitions.
4. In the event of subject death during the conduct of the study, efforts should be made to perform an autopsy.
5. Sensations or side effects that occur during the programming session should not be reported as AEs. However, undesired sensations or side effects caused by the final programming parameters (including active contact, pulse width, frequency, and amplitude) that persist or occur after the completion of the programming should be reported as AEs.

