6. Lack of efficacy/decreased therapeutic response should not be reported as AEs. Clinical sequelae, other than pain, that occur as a result of lack of efficacy/decreased therapeutic response should be reported as AEs
7. Clinically significant worsening of the pattern of intensity or distribution of Baseline pain symptoms should be reported as an AE.
8. Device deficiencies, including, but not limited to device/lead migrations, which are not associated with an adverse clinical outcome should only be reported as device deficiencies. However, if a device deficiency precipitates an AE, the AE should be reported in the *Adverse Event* eCRF and the device deficiency should be documented in the *Device Deficiency* eCRF.

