20.3 Investigator Reporting Requirements

The communication requirements for reporting to BSC are as shown in **Error! Reference source not found.**3.

Table 20-3: Investigator Reporting Requirements

Unanticipated Serious Adverse Device Effect	Complete AE eCRF page with all available new and updated information	
• Within 1 business day of first becoming aware of the event.• Terminating at the end of the study
---	--	---

Table 20-3: Investigator Reporting Requirements

Serious Adverse Event including Serious Adverse Device Effects	Complete AE eCRF page with all available new and updated information	
 Within 2 business days of first becoming aware of the event or as per local/regional regulations. Reporting required through the end of the study
	Provide all relevant source documentation (unidentified) for reported event	
 When documentation is available
Adverse Event	Complete AE eCRF page, which contains such information as date of AE, treatment of AE resolution, assessment of seriousness and relationship to the device	
 In a timely manner (e.g. Recommend within 10 business days) after becoming aware of the information Reporting required for adverse events related to procedure, hardware and stimulation. Reporting is required through the end of the study.
Device Deficiencies (including but not limited to failures, malfunctions, and product nonconformities) Note: Any Investigational Device Deficiency that might have led to a serious adverse event if a) suitable action had not been taken or b) intervention had not been made or c) if circumstances had been less fortunate is considered a reportable event.	Complete Device Deficiency eCRF with all available new and updated information	
 Within 2 business day of first becoming aware of the event and as per local/regional regulations Reporting required through the end of the study

Note:

- AEs related to device/procedure, SAEs, SADEs, Device Deficiencies and USADEs will be collected from the time of informed consent through end of study. SAEs and Device Deficiencies may be reported via phone, fax or email if the electronic data capture (EDC) system is unavailable. The paper SAE Notification Form or Device Deficiency Notification Form should be used to report SAEs and/or device deficiencies during this time.

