20.4 Boston Scientific Device Deficiencies

All device deficiencies (including but not limited to failures, malfunctions, use errors, product nonconformities, and labeling errors) will be documented and reported to BSC. If possible, the device(s) should be returned to BSC for analysis. Instructions for returning the investigational device(s) will be provided. If it is not possible to return the device, the investigator should document why the device was not returned and the final disposition of the device. Device failures and malfunctions should also be documented in the subject's medical record.

Boston Scientific will be notified of all device deficiencies, failures, malfunctions and product nonconformities with respects to the products in use in the study. Report all these events in the appropriate eCRF.

Device deficiencies (including but not limited to failures, malfunctions, and product nonconformities) are not to be reported as adverse events. However, if there is an adverse event that results from a device failure or malfunction, that specific event would be recorded on the appropriate eCRF.

And, any Investigational Device Deficiency that might have led to a serious adverse event if a) suitable action had not been taken or b) intervention had not been made or c) if circumstances had been less fortunate is considered a reportable event.

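### An uncomplicated revision after lead migration can be absent from the stated safety rates; separately, 20.1 and Table 20-3 differ on which adverse events are recorded

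*Combined protocol and SAP*

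**What the plan says.** **Deficiencies and loss of effect.** Section 20.1, Note 8 directs that device deficiencies, "including, but not limited to device/lead migrations, which are not associated with an adverse clinical outcome should only be reported as device deficiencies". If a deficiency leads to an AE, both forms are completed. Section 20.4 agrees: "Device deficiencies (including but not limited to failures, malfunctions, and product nonconformities) are not to be reported as adverse events". Note 6 states "Lack of efficacy/decreased therapeutic response should not be reported as AEs" but also "Clinical sequelae, other than pain, that occur as a result of lack of efficacy/decreased therapeutic response should be reported as AEs". Note 7 adds "Clinically significant worsening of the pattern of intensity or distribution of Baseline pain symptoms should be reported as an AE". Notes 2 and 3 exempt planned or elective admissions from SAE reporting, but not complications that arise during them.

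**What is collected.** Section 11.11 foresees repositioning or replacement of leads, extensions and IPGs and requires each to be documented. The Device Deficiencies row of Table 20-3 requires sites to "Complete Device Deficiency eCRF with all available new and updated information".

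**What is counted.** The synopsis, 7.5 and 12.5 give the same list: device- or procedure-related AEs, SAEs including SADEs, and USADEs. None names revisions, explants or deficiencies. Section 12.5 plans Kaplan-Meier plots and Cox models but names no time-to-event variable.

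**Scope of AE recording.** Section 20.1 requires any AE after consent to be entered in the eCRF, and 20.2 requires relatedness to be assessed for all AEs. The Adverse Event row of Table 20-3 requires reporting of AEs related to procedure, hardware or stimulation. The note under the table limits collection to related AEs, SAEs, SADEs, USADEs and device deficiencies.

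**The concern.** The stated aim is to characterize real-world outcomes of an implanted system, and re-operation is part of what such a system costs the patient. If a site follows the reporting rules as written, a subject can return to surgery for a migrated lead and add nothing to any safety rate in the readable plan. The published rates could then look better than the surgical record.

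The second issue is separate. If one site enters every AE and another enters only those it judges related, the AE data sets of the two sites differ in kind. A non-serious event first judged unrelated may never reach the sponsor's safety evaluation described in 22.1, so the relatedness call cannot be looked at again.

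**Working it through.** The documents give no migration, revision or deficiency rate, so there is no figure to reproduce. The check is to follow one event through the rules.

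**Part 1: a migrated lead, pain back at its Baseline level and site, lead repositioned without complication**

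1. *Is the migration an AE?* Under Note 8 and 20.4, no, provided the site judges that it had no adverse clinical outcome. The text does not define that condition.
2. *Is the lost relief an AE?* Under Note 6, no. Note 7 applies to worsening of Baseline pain, and a return to Baseline is not clearly that.
3. *Is the surgery an AE or SAE?* A planned admission need not be an SAE (Notes 2 and 3). A complication would be reportable, but here there is none.
4. *Is there an SAE, SADE or USADE?* Table 20-1 builds each of these on an AE. Without an AE, none arises.
5. *What exists on file?* A Device Deficiency eCRF and the documentation required by 11.11.
6. *Contribution to the 7.5 and 12.5 rates:* 0.

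**Routes that would still produce an AE**

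- Note 5: "undesired sensations or side effects caused by the final programming parameters" that persist or occur after programming is complete.
- Note 6: sequelae other than pain.
- Note 7: pain worse than Baseline, or in a new distribution.
- Note 8: any AE that the deficiency precipitates.
- Notes 2 and 3: surgical complications.
- The general rule in 20.1: "Underlying diseases are not reported as AEs unless there is an increase in severity or frequency during the course of the investigation". This is not tied to Baseline, and the text does not say whether Note 6 overrides it for returning pain.

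**Scale**

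- One subject among 60 implanted (the cap in 10.4): 1/60 = 1.67 percentage points.
- The safety set in 12.6.1 is all consented subjects, and its size is not given. Assuming 60 to 100 consent: 1/60 = 1.67, 1/80 = 1.25, 1/100 = 1.00 points.
- Ceiling on the number affected, at assumed true revision rates p: expected revisions are 60p and the chance of at least one is 1 − (1 − p)^60.

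| Assumed p | Expected revisions of 60 | Chance of at least one |
|---|---|---|
| 1% | 0.6 | 45% |
| 2% | 1.2 | 70% |
| 5% | 3 | 95% |
| 10% | 6 | 99.8% |
| 20% | 12 | >99.9% |

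These are all revisions. Those on the narrow pathway are an unknown subset, so the table bounds the omission and does not estimate it.

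**Part 2: AE scope by type of event**

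| Event | 20.1 | Table 20-3 and note |
|---|---|---|
| Related AE | recorded | reported and collected |
| SAE, SADE, USADE | recorded | reported and collected |
| Non-serious AE judged unrelated | recorded | not named |

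Only the last row differs. Such events fall outside the related-AE rate in 7.5, so the direct effect on that rate is 0 points.

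**The case against.** *Much of the plan is hidden.* Secondary, exploratory and health-economic endpoints are redacted, the assessment descriptions in 13.2 cannot be read, and 12.5 uses open wording for its list. A revision count may sit in any of these, or among the unnamed time-to-event variables. This stands. A reader might infer that the plan counts revisions nowhere; the documents do not support that. The safety parameters themselves are readable, however, and they do not name revisions.

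*The pathway needs many conditions at once, and other text would catch most cases.* This also stands in large part. Section 11.10 lists revision and replacement among the reasons for unscheduled visits, and Table 11-1 requires AE assessment at those visits. That prompts the question but does not change the answer, because Notes 6 to 8 still govern what is entered. A reader might infer that revisions in general go uncounted; the open AE routes rule that out.

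*The data are collected.* Correct. It would be wrong to infer that re-operations go unrecorded. The gap is in the planned count.

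*Table 20-3 is about reporting and 20.1 about recording.* This does not reconcile them. Reporting under the table means completing the AE eCRF page, and the note speaks of what is collected. Section 17.2 asks investigators to record every AE as the protocol applies, which does not say which of the two scopes applies.

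**Conclusion.** Both parts hold in a limited form.

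On part 1, the readable safety rates can omit an uncomplicated re-operation for a migrated lead. The omission is 1.7 points of 60 implanted for each such subject, with the number of subjects unknown. It rests on a site finding no adverse clinical outcome under Note 8, on no other AE route applying, and on no redacted endpoint already counting revisions. It does not follow that lost response is hidden from the efficacy results: 11.11 keeps revised subjects' effectiveness data in the intent-to-treat analysis.

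On part 2, the sections conflict for non-serious AEs judged unrelated. The consequence is uneven capture between sites and possible loss of events from later safety review. A reader might infer that the conflict biases the planned related-AE rate; by definition it does not do so directly.

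The sponsor should act on both, with medium confidence given the redactions.

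**What to change.** **Part 1.** In 7.5 and 12.5, add for implanted subjects:

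- the proportion with any surgical revision, replacement or explant, with an exact 95% confidence interval (for scale, an assumed 3 of 60 would read 5.0%, interval 1.0 to 13.9%);
- the device-deficiency rate including lead migration, whether or not an AE was recorded.

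State the implanted denominator, because only these subjects can have a revision: an assumed 6 revisions are 10.0% of 60 implanted but 7.5% of 80 consented. Draw the counts from the 11.11 documentation and the Device Deficiency eCRF. Beside the revision figure, show the number withdrawn for declining a recommended revision; 10.2 already requires withdrawal reasons to be reported and lists this one. If a redacted endpoint already counts revisions, a cross-reference is enough.

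**Part 2.** Reconcile 20.1, 20.2 and Table 20-3 with its note, so that one AE recording scope applies at all sites.

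**Cost.** Two more tables and possibly a less favourable safety figure. A revision record must also be identified: Table 11-1 schedules procedure information only at implant, 11.11 names no form, and the description in 13.2.10 cannot be read. If the wider AE scope is kept, sites enter somewhat more AEs.

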20.2 Relationship to Study Device(s)

The Investigator must assess the relationship of the AE to the study device or procedure. See criteria in **Error! Reference source not found.**

Table 20-2: Criteria for Assessing Relationship of Study Device or Procedure to Adverse Event

Classification	Description
Unrelated	The adverse event is determined to be due to a concurrent illness or effect of another device/drug and is not related to the investigational product.
Related	d) The adverse event is determined to be potentially related to the investigational product, and an alternative etiology is equally or less likely compared to the potential relationship to investigational product, or e) There is a strong relationship to investigational product, or recurs on re-challenge, and another etiology is unlikely, or There is no other reasonable medical explanation for the event.

The Investigator must assess the potential relationship of all adverse events to the **device and procedure**. All **device** related adverse events will be assessed according to their relationship to one of the following sub-categories:

- **Device Hardware-Related AEs:** AEs that can reasonably be attributed to the mere physical presence of the device or to deficiency of the device (i.e., an allergic response to device materials).
- **Stimulation-Related AEs:** AEs that can reasonably be attributed to the effects of stimulation. A relationship to stimulation may be determined by demonstrating a predictable response to the alternating between stimulation-on and stimulation-off settings. However, a relationship to stimulation may also be reported without demonstrating a predictable response to the alternating between the stimulation-on and stimulation-off settings if in the opinion of the Investigator the AE is potentially related to stimulation.
- **Procedure Related AEs:** AEs that can reasonably be attributed to a **study protocol required procedure**.

20.3 Investigator Reporting Requirements

The communication requirements for reporting to BSC are as shown in **Error! Reference source not found.**3.

Table 20-3: Investigator Reporting Requirements

Unanticipated Serious Adverse Device Effect	Complete AE eCRF page with all available new and updated information	
• Within 1 business day of first becoming aware of the event.• Terminating at the end of the study
---	--	---

Table 20-3: Investigator Reporting Requirements

Serious Adverse Event including Serious Adverse Device Effects	Complete AE eCRF page with all available new and updated information	
 Within 2 business days of first becoming aware of the event or as per local/regional regulations. Reporting required through the end of the study
	Provide all relevant source documentation (unidentified) for reported event	
 When documentation is available
Adverse Event	Complete AE eCRF page, which contains such information as date of AE, treatment of AE resolution, assessment of seriousness and relationship to the device	
 In a timely manner (e.g. Recommend within 10 business days) after becoming aware of the information Reporting required for adverse events related to procedure, hardware and stimulation. Reporting is required through the end of the study.
Device Deficiencies (including but not limited to failures, malfunctions, and product nonconformities) Note: Any Investigational Device Deficiency that might have led to a serious adverse event if a) suitable action had not been taken or b) intervention had not been made or c) if circumstances had been less fortunate is considered a reportable event.	Complete Device Deficiency eCRF with all available new and updated information	
 Within 2 business day of first becoming aware of the event and as per local/regional regulations Reporting required through the end of the study

Note:

- AEs related to device/procedure, SAEs, SADEs, Device Deficiencies and USADEs will be collected from the time of informed consent through end of study. SAEs and Device Deficiencies may be reported via phone, fax or email if the electronic data capture (EDC) system is unavailable. The paper SAE Notification Form or Device Deficiency Notification Form should be used to report SAEs and/or device deficiencies during this time.
- Subjects should be instructed to contact their physician immediately if they experience any adverse event rather than wait for a scheduled visit.

20.4 Boston Scientific Device Deficiencies

All device deficiencies (including but not limited to failures, malfunctions, use errors, product nonconformities, and labeling errors) will be documented and reported to BSC. If possible, the device(s) should be returned to BSC for analysis. Instructions for returning the investigational device(s) will be provided. If it is not possible to return the device, the investigator should document why the device was not returned and the final disposition of the device. Device failures and malfunctions should also be documented in the subject's medical record.

Boston Scientific will be notified of all device deficiencies, failures, malfunctions and product nonconformities with respects to the products in use in the study. Report all these events in the appropriate eCRF.

Device deficiencies (including but not limited to failures, malfunctions, and product nonconformities) are not to be reported as adverse events. However, if there is an adverse event that results from a device failure or malfunction, that specific event would be recorded on the appropriate eCRF.

And, any Investigational Device Deficiency that might have led to a serious adverse event if a) suitable action had not been taken or b) intervention had not been made or c) if circumstances had been less fortunate is considered a reportable event.

20.5 Reporting to Regulatory Authorities / IRBs / ECs / Investigators

BSC is responsible for reporting adverse event information to all participating Principal Investigators and regulatory authorities, as applicable.

The Principal Investigator is responsible for informing the EC, and regulatory authorities of UADE and SAE as required by local/regional regulations.

21 Informed Consent

Subject participation in this clinical study is voluntary. Informed Consent is required from each subject or his/her legally authorized representative. The Investigator is responsible for ensuring that Informed Consent is obtained prior to the use of any investigational devices, study-required procedures and/or testing, or data collection.

The obtaining and documentation of Informed Consent must be in accordance with the principles of the Declaration of Helsinki, ISO 14155, any applicable national regulations, and local Ethics Committee and/or Regulatory authority body, as applicable. The ICF must be accepted by BSC or its delegate (e.g. CRO), and approved by the site's IRB/EC, or central IRB, if applicable.

Boston Scientific will provide a study-specific template of the ICF to investigators participating in this study. The ICF template may be modified to meet the requirements of the investigative site's IRB/EC. Any modification requires acceptance from BSC prior to use of the form. The ICF must be in a language understandable to the subject and if needed, BSC will assist the site in obtaining a written consent translation. Translated consent forms must also have IRB/EC approval prior to their use. Privacy language shall be included in the body of the form or as a separate form as applicable.

The process of obtaining Informed Consent shall at a minimum include the following steps, as well as any other steps required by applicable laws, rules, regulations and guidelines:

- be conducted by the Principal Investigator or designee authorized to conduct the process,
- include a description of all aspects of the clinical study that are relevant to the subject's decision to participate throughout the clinical study,
- avoid any coercion of or undue influence of subjects to participate,
- not waive or appear to waive subject's legal rights,
- use native language that is non-technical and understandable to the subject or his/her legal representative,
- provide ample time for the subject to consider participation and ask questions if necessary,
- ensure important new information is provided to new and existing subjects throughout the clinical study.

The ICF shall always be signed and personally dated by the subject or legal representative competent to sign the ICF under the applicable laws, rules, regulations and guidelines and by the investigator and/or an authorized designee responsible for conducting the informed consent process. If a legal representative signs, the subject shall be asked to provide informed consent for continued participation as soon as his/her medical condition allows. The original signed ICF will be retained by the site and a copy of the signed and dated document and any other written information must be given to the person signing the form.

Failure to obtain subject consent will be reported by BSC to the applicable regulatory body according to their requirements (e.g., FDA requirement is within 5 working days of learning of such an event). Any violations of the informed consent process must be reported as deviations to the sponsor and local regulatory authorities (e.g. IRB/EC), as appropriate.

If new information becomes available that can significantly affect a subject's future health and medical care, that information shall be provided to the affected subject(s) in written form via a revised ICF or, in some situations, enrolled subjects may be requested to sign and date an addendum to the ICF. In addition to new significant information during the course of a study, other situations may necessitate revision of the ICF, such as if there are amendments to the applicable laws, protocol, a change in Principal Investigator, administrative changes, or following annual review by the IRB/EC. The new version of the ICF must be approved by the IRB/EC. Acceptance by Boston Scientific is required if changes to the revised ICF are

requested by the site's IRB/EC. The IRB/EC will determine the subject population to be re-consented.

Study personnel should explain that even if a subject agrees to participate in the study and signs an Informed Consent form, screening procedures may demonstrate that the subject is not a suitable candidate for the study.

22 Committees

